4.4. Pharmacokinetic (PK) and PK/Pharmacodynamic (PD) Hypotheses

Not applicable.

5. PLANNED ANALYSES

5.1. Interim Analyses

NA

5.2. Final Analysis

The study is terminated early with 5 treated patients and the planned analyses specified in the protocol will not be performed. Only selected analyses will be provided to support synoptic CSR.

6. ANALYSES POPULATION

6.1. Enrolled Population

Enrolled population will include all subjects who enrolled in the study.

6.2. Safety Population

Safety population will include all subjects who received at least 1 dose of study drug and have at least 1 post-baseline safety evaluation, regardless of mutation status. This will be the analysis set for all evaluation in the final analysis.

7. GENERAL CONSIDERATIONS FOR DATA ANALYSES AND HANDLING

7.1. Baseline Definition

Baseline is defined as the last non-missing (including unscheduled) assessment value prior to the initial administration of the study drug. If an assessment is performed on the same day as the first dose of study drug, and time is not collected, the assessment will be considered baseline. If there is more than one value on or prior to the initial administration of the study drug, the value closest to and prior to the receipt of the first dose, whether scheduled or unscheduled, will be used as the baseline value.

AEs and medications reported with a start date on the date of first dose will be considered to have occurred after the start of treatment. For vital signs (excluding weight and height) and ECG measures, baseline results will be identified for the set. Baseline will be determined separately for each laboratory analyte.

7.2. Derived and Transformed Data

7.2.1. Baseline Age

Subject's age in years will be calculated based on date of informed consent date using the following formula:

Age (year) = FLOOR ((date of informed consent – date of birth)/365.25*12)

where FLOOR() function returns the integer part of the result.

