8.1. Study Population

8.1.1. Inclusion Criteria

- 1. Men and women of 18 years of age and older
- 2. Voluntary agreement to provide written informed consent and the willingness and ability to comply with all aspects of the protocol
- 3. Eastern Cooperative Oncology Group (ECOG) score of 0, 1, or 2 (Appendix 1)
- 4. Life expectancy (in the opinion of the Investigator) of ≥ 3 months before enrollment
- 5. Have histologically confirmed FL, Grade 1 to 3a. Subjects may have R/Rdisease following at least 2 standard prior systemic treatment regimens where at least 1 anti-CD20-based regimen was used
- 6. Treatment recommended in accordance with the Groupe d'Etude des Lymphomes Folliculaires (GELF) criteria due to the presence of at least one of the following:
 - a. Any nodal or extranodal tumor mass >7 cm diameter
 - b. Involvement of at least 3 nodal sites, each with diameter >3 cm
 - c. Presence of any systemic or B symptoms
 - d. Splenic enlargement with inferior margin below the umbilical line
 - e. Compression syndrome (ureteral, orbital, gastrointestinal)
 - f. Pleural or peritoneal serous effusion (irrespective of cell content)
 - g. Leukemic phase (>5.0 x 10⁹/L circulating malignant cells)
 - h. Cytopenias (granulocyte count $\leq 1.0 \times 10^9/L$ and/or platelets $\leq 100 \times 10^9/L$)
- 7. Meet the following laboratory parameters:
 - a. Absolute neutrophil count (ANC) \geq 750 cells/ μ L (0.75 x 10⁹/L), or \geq 500 cells/ μ L (0.50 x 10⁹/L) in subjects with documented bone marrow involvement
 - b. Platelet count $\geq 50,\!000$ cells/µL (50 x 109/L), or $\geq 30,\!000$ cells/µL (30 x 109/L) in subjects with documented bone marrow involvement, and without transfusion dependence
 - c. Hemoglobin $\geq 8 \text{ g/dL}$
 - d. Serum alanine aminotransferase (AST) and aspartate aminotransferase (ALT) \leq 3.0 x ULN, unless related to disease involvement
 - e. Total bilirubin ≤ 1.5 x ULN, unless due to disease involvement, Gilbert's syndrome, or hemolytic anemia

- f. Estimated creatinine clearance (ie, estimated glomerular filtration rate [eGFR] using Cockcroft-Gault [Appendix 4]) ≥ 40 mL/min
- 8. At least one bi-dimensionally measurable nodal lesion > 1.5 cm in its longest diameter by computed tomography (CT) scan or magnetic resonance imaging (MRI) excluding lesions that meet the following criteria:
 - a. Previously irradiated lesions should not be counted as target lesions

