8. STATISTICAL ANALYSIS

This study was early terminated. Given there were only 5 subjects enrolled, only selected safety analyses will be done based on safety population. No futility analysis or efficacy analysis will be performed.

All summary tables will have column 'Total' only.

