8.3. Demographic and Baseline Characteristics

The following variables will be summarized to describe the demographics and other baseline disease characteristics at enrollment:

- Age summarized as a continuous variable in years relative to the date informed consent is signed. Age will also be summarized categorically based on the following age groups: ≥ 65 years and < 65 years
- Sex (male, female)
- race (American Indian or Alaska Native, Asian, Black or African American, Native Hawaiian or Other Pacific Islander, White, Other/Unknown)
- ethnicity (Hispanic or Latino, not Hispanic or Latino, Not Reported)
- Tumor type (Follicular Lymphoma, Other) and Grade
- Number of prior lines of anticancer therapy as a continuous variable and also summarized categorically based on the categories: ≤ 2 , 3, 4, ≥ 5
- Best response to prior anticancer therapy (Complete response, Partial response, Progressive disease, Not evaluable, Unknown)

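### The SAP formula for age in years multiplies by 12 and returns months; programmed as written, it puts every eligible subject in the 65-and-over group

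*SAP*

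**What the plan says.** SAP Section 7.2.1 (Baseline Age) states the intended unit: "Subject's age in years will be calculated based on date of informed consent date using the following formula". The formula that follows is "Age (year) = FLOOR ((date of informed consent – date of birth)/365.25*12", with a closing bracket after the 12. The section adds "where FLOOR() function returns the integer part of the result", so the function truncates and does nothing else.

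SAP Section 8.3 (Demographic and Baseline Characteristics) uses the result twice. The first use is "Age summarized as a continuous variable in years relative to the date informed consent is signed". The second is "Age will also be summarized categorically based on the following age groups: ≥ 65 years and < 65 years".

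The lower age limit is in Protocol Section 8.1.1, inclusion criterion 1: "Men and women of 18 years of age and older". On what will be run after early termination, SAP Section 8 says "Given there were only 5 subjects enrolled, only selected safety analyses will be done based on safety population". Demographics remain among the planned summaries.

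**The concern.** The label and the arithmetic in Section 7.2.1 disagree. Days divided by 365.25 are years, and multiplying by 12 gives months. Nothing later in the SAP divides by 12 again, and the 65 cut in Section 8.3 is stated in years.

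A program that follows the SAP would therefore report a continuous age summary about twelve times too large, and an age-group table with nobody under 65. The grouping would be wrong for each subject truly under 65, and right for the others only by accident. With no efficacy analysis and the safety data given as listings, the demographic table is one of the few summaries left for the synoptic CSR. If all 5 subjects are in the Safety Population, each misclassified subject moves the age-group split by 1/5 = 20 percentage points.

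**Working it through.** The documents give no numerical age that depends on this formula, so there is no stated figure to reproduce. The check evaluates the formula itself.

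**Inputs**
- Formula and intended unit (years): SAP Section 7.2.1.
- Uses of age (continuous in years; split at 65): SAP Section 8.3.
- Minimum age of 18: Protocol Section 8.1.1.
- Number of subjects, 5: SAP Section 8.
- Assumption, for illustration only: consent on 15 January 2022, falling on the subject's birthday. The documents give no subject's dates.

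**Three forms compared**, where d is the number of days from birth to consent:
- (a) as written, evaluated left to right: FLOOR(d/365.25 × 12)
- (b) the other possible grouping: FLOOR(d/(365.25 × 12)) = FLOOR(d/4383)
- (c) without the factor of 12: FLOOR(d/365.25)

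| True age | d | (a) as written | (b) regrouped | (c) without 12 |
|---|---|---|---|---|
| 18 | 6575 | 216 | 1 | 18 |
| 30 | 10958 | 360 | 2 | 30 |
| 45 | 16436 | 539 | 3 | 44 |
| 64 | 23376 | 768 | 5 | 64 |
| 65 | 23741 | 779 | 5 | 64 |
| 80 | 29220 | 960 | 6 | 80 |
| 100 | 36525 | 1200 | 8 | 100 |

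**Where form (a) crosses 65.** Setting d/365.25 × 12 = 65 gives a true age of 65/12 = 5.42 years. Every adult is far beyond that. At the eligibility minimum the value is 6575/365.25 × 12 = 216.02, which truncates to 216. If the 18 years contain only four leap days, d = 6574 and the value is 215.98, which truncates to 215. Either way the under-65 group cannot contain an eligible subject.

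**Form (b) does not rescue the formula.** It would need a true age of 65 × 12 = 780 years to reach 65, so it would put every subject under 65. Neither grouping returns years.

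**Form (c) returns years, with one small artefact.** On an exact birthday it can be one year low: at 65, 23741/365.25 = 64.9993, which truncates to 64, and one day later 23742 days gives 65. The 45-year row shows the same effect. This belongs to the 365.25 convention and is separate from the factor of 12.

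**The case against.** The strongest reply concedes the slip and argues that it hardly matters. The intended unit is stated in the sentence before the formula, in the formula's own label and again in Section 8.3, so a programmer would know what was meant. Ages such as 216 or 720 are impossible and would be noticed at once. Protocol Section 12.1.1 lists age among the demographic items collected at screening, which should allow a cross-check. Age enters no hypothesis test, response rate, stopping rule, exposure measure or adverse event listing. The documents give no subject's age, so the number truly under 65, and hence misclassified, is unknown and could be zero. The analysis set also requires a post-baseline safety evaluation (SAP Section 6.2), so 5 is an upper bound.

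Most of this stands as a limit on consequence. The harm is confined to descriptive age rows in at most 5 subjects, and an undetected wrong table is unlikely. The factor of 12 is also approximate once truncation is allowed for: a subject aged 60 would show as 720 up to about 731 during that year of age.

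None of it makes the formula right. Relying on someone to notice is not a specification. SAP Section 2 says the SAP supersedes the protocol's statistical considerations and requires any deviation from it to be justified in the synoptic CSR. A programmer who quietly drops the factor is therefore departing from the governing document without the required record. Nor does the protocol offer another derivation to fall back on.

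**Conclusion.** The point holds. As written, the formula returns completed months under a label of years, and no other section corrects it. Followed literally, it inflates the continuous age summary about 12-fold and places every eligible subject in the 65-and-over group, because the smallest value an eligible subject can produce is about 216.

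This rests on ordinary operator precedence, on the 18-year eligibility minimum and on the SAP being programmed as it stands. The number of subjects actually misclassified equals the number truly under 65, which lies between 0 and 5 and cannot be known from the documents. No inferential, efficacy or safety conclusion depends on the error. It still needs correcting, because it is a stated derivation rule that gives a wrong result in an output that will be produced.

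**What to change.** In SAP Section 7.2.1, delete the factor of 12:

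Age (years) = FLOOR((date of informed consent − date of birth)/365.25)

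A calculation that counts completed birthdays at the consent date is slightly better. It also removes the one-day artefact, which would otherwise fall on the 65 cut for a subject consenting on a 65th birthday. Section 8.3 needs no change.

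The cost is one line in the SAP and the matching line of code. If the SAP can no longer be amended, record the corrected derivation as a deviation in the synoptic CSR, as SAP Section 2 requires. In either case, check the derived ages against any age recorded at screening before the demographic table is finalised.

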7.2.2. Study Day

If the date of interest occurs on or after the first dose then study day will be calculated as (date of interest – date of first dose) + 1. If the date of interest occurs prior to the first dose date then study day will be calculated as (date of interest – date of first dose). There is no study day 0.

7.2.3. Change from Baseline

NA

7.2.4. Completers

All subjects discontinued the study.

8. STATISTICAL ANALYSIS

This study was early terminated. Given there were only 5 subjects enrolled, only selected safety analyses will be done based on safety population. No futility analysis or efficacy analysis will be performed.

All summary tables will have column 'Total' only.

8.1. Disposition of Subjects

The number of subjects enrolled will be summarized based on the following categories:

- Enrolled population
- Safety population
- Study drug ongoing/completed/discontinued (including reason)
- Study ongoing/completed/discontinued (including reason)

A subject listing of disposition information will also be presented for the safety population.

8.2. Protocol Deviations

No protocol deviation information collected at the time of study termination.

8.3. Demographic and Baseline Characteristics

The following variables will be summarized to describe the demographics and other baseline disease characteristics at enrollment:

- Age summarized as a continuous variable in years relative to the date informed consent is signed. Age will also be summarized categorically based on the following age groups: ≥ 65 years and < 65 years
- Sex (male, female)
- race (American Indian or Alaska Native, Asian, Black or African American, Native Hawaiian or Other Pacific Islander, White, Other/Unknown)
- ethnicity (Hispanic or Latino, not Hispanic or Latino, Not Reported)
- Tumor type (Follicular Lymphoma, Other) and Grade
- Number of prior lines of anticancer therapy as a continuous variable and also summarized categorically based on the categories: ≤ 2 , 3, 4, ≥ 5
- Best response to prior anticancer therapy (Complete response, Partial response, Progressive disease, Not evaluable, Unknown)

8.4. Prior Cancer Therapy

Prior Cancer therapy will be summarized for the following variables:

- Number of prior lines of anticancer therapy will be summarized as a continuous variable and also categorically based on the categories: ≤ 2 , 3, 4, ≥ 5

- Best response to prior anticancer therapy (Complete response, Partial response, Progressive disease, Not evaluable, Unknown)

A by-subject listing will be also provided.

8.5. Prior and Concomitant Medications

A by-subject listing will be provided for prior and concomitant medications

8.6. Exposure and Treatment Compliance

The following variables will be summarized for exposure and treatment compliance of Tazemetostat and Rituximab:

- Duration of tazemetostat/rituximab summarized as continuous variable and as categorical variables
- Number of cycles initiated for tazemetostat/rituximab
- Total amount of tazemetostat/rituximab taken (mg)
- Average dose intensity of tazemetostat/rituximab (mg BID/day)
- Percentage of tazemetostat/rituximab taken
- Category of percentage of drug taken

9. EFFICACY ANALYSES

No efficacy analysis will be performed.

10. SAFETY ANALYSES

All the safety measurements will be listed in the listings for safety population.

10.1. Adverse Events

The following AE listings will be provided:

- All adverse events
- All serious adverse events (SAEs)
- Treatment emergent adverse events (TEAEs)
- Treatment emergent SAEs
- TEAEs leading to discontinuation of study drug

10.2. Clinical Laboratory Evaluations

The following listings will be provided for clinical laboratory evaluations:

- Laboratory Data – Hematology
- Laboratory Data – Blood chemistry and coagulation
- Laboratory Data – Urinalysis
- Grades 3 and 4 Laboratory Data - Hematology
- Grades 3 and 4 Laboratory Data - Blood Chemistry and Coagulation
- Laboratory Results $< 0.25 \times \text{LLN}$ or $> 2.5 \times \text{ULN}$ – Hematology
- Laboratory Results $< 0.25 \times \text{LLN}$ or $> 2.5 \times \text{ULN}$ - Blood Chemistry and Coagulation

10.3. Other Safety Measures

The following listings will be provided for ECG and Vital sign:

- 12-lead Electrocardiogram
- Vital Signs

12. APPENDIX

CCI
